(iii) Given the expected bias in treatment selection and to further enhance our ability of obtaining accurate statistical inferences, we will use propensity scores. Propensity scores will estimate the probability on the basis of all patients and center characteristics that patients would proceed to allogeneic HCT with the use of proportional hazard model to adjust for between-group differences in the previously mentioned characteristics.[112] The magnitude of divergence of propensity scores between the two approaches will allow us to assess the amount of bias in treatment selection. Inverse-probability-weighting based on the propensity score will then be used as a secondary tool to adjust for differences between the two treatment-groups [113]. This approach will be implemented to create balance and it involves weighting each patient who received HCT by the inverse of the probability that he or she would be selected for HCT and weighting each patient who received conventional treatment by the inverse of the probability that he or she would be selected for conventional treatment. We will verify the performance of the propensity model by comparing the distribution of covariates and propensity scores between treatment groups both before and after inverse probability weighting.[114] Adjusted OS curves will be estimated using the inverse-probability-weighting approach of Cole and Hernan.[115] Assessment of benefit of either approach will be done in quintiles of propensity scores.

(iv) Sensitivity analyses will be performed to better understand any statistical disagreement between the models. First, OS curves for comparing both groups will be estimated using a double robust strategy of combining the inverse-probability weighting with the regression-based estimation [116]. Secondly, propensity scores will be used to construct matched samples from both groups to be used for simple matched pair analyses which adjust for confounding variables. Finally, we will use the method of Lin et al [117] to assess whether the observed differences in the rate of death could be due to an unmeasured confounder.

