(3) Secondary Outcomes: **(i)** The relationship between the choice of treatment (HCT vs. non-HCT) and QOL, function, utilization, and satisfaction scores will be examined. Intra-patient differences will be used to analyze changes in QOL from baseline to follow-up assessments. Basic analyses will utilize paired t-tests (for changes over time) and two-sample t-tests (for comparison between groups). In order to make full use of the longitudinal data we will also use generalized estimating equations (GEEs) approach,[118] which can accommodate the within patient correlation structure and arbitrary patterns of missing data. Further, the GEEs approach would allow for the population-average interpretation which is an advantage over, for example, generalized linear mixed models approach.

(ii) The previously described statistical approaches will be used to adjust the comparisons between recipients of allogeneic HCT and conventional therapy for the pre-exposure measures of QOL and preference scores.

(iii) We will compare the quality-adjusted outcomes using the Q-TWiST methodology which weights survival time according to clinical status (alive without relapse or toxicity, relapse, and toxicity) [119-122]

(4) Tertiary Outcomes: **(i)** The risk factors for mortality after ICU admission in patients with AML will be examined. Survival analysis with logistic regression or Cox proportional hazards model will be used, depending on completeness of patient follow-up. Variables in the model will include the AML-comorbidity model score, history of HCT, AML disease status, absolute neutrophil count, use of life support devices, bacteremia, and creatinine. The above risk factors will be evaluated using AUC and c-statistic to inform development of a potential model to predict ICU mortality. **(ii)** The outcomes of patients with secondary AML will be evaluated as compared to patients with primary AML, after adjusting for percent blasts in the peripheral blood, white blood cell count, and performance status at time of presentation.

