11.4 Missing Data

Protocol 2368.00

This specific aim depends on a high response rate from patients in providing data. The PI together with the SCCA data coordinator will monitor compliance with the self-reported data on a monthly basis and institute corrective measures if the response rate falls below 75%. These may include closer tracking of patients to make sure clinically significant time points are recognized and evaluation of factors associated with no-response in order to identify populations which require greater efforts. Upon receipt of patient-reported data, completion of individual items will be assessed immediately, so that missing data can be requested.

The linear mixed models analysis will be able to accommodate arbitrary patterns of missing data; however, graphical presentations and logistic regression analysis will be performed to understand the missing data mechanism as well as to identify factors associated with incomplete data for survivors. Plots of change in QOL scores from baseline to 90 days, 6 months, 1-year, and 2-year stratified by time of drop-out will be generated separately for each group to determine pattern of missing data. Logistic regression will be used to identify baseline and clinical characteristics associated with missing data. All demographics and baseline characteristics will be included in the logistic model.

Protocol 2368.00

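### The longitudinal QOL analysis claims protection against missing data that an unweighted GEE does not have, and Section 11.4 relies on a mixed model that no section defines

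*Combined protocol and SAP*

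**What the plan says.** Objective 5.1.2.2 lists QOL under the primary objectives; Section 11.3(3) analyses it as a secondary outcome.

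- **Section 11.3(3)(i)** plans t-tests as the basic analysis and adds GEE to use the longitudinal data, as an approach "which can accommodate the within patient correlation structure and arbitrary patterns of missing data". It prefers GEE to generalized linear mixed models for its population-average interpretation. It names no working correlation and no missing-data assumption.
- **Section 11.3(3)(ii)** adjusts the group comparison "for the pre-exposure measures of QOL and preference scores".
- **Section 11.3(2)(iii)** contains the plan's only weights, and they concern treatment selection: "Inverse-probability-weighting based on the propensity score will then be used as a secondary tool to adjust for differences between the two treatment-groups".
- **Section 11.4** states: "The linear mixed models analysis will be able to accommodate arbitrary patterns of missing data". It plans plots of QOL change "stratified by time of drop-out will be generated separately for each group to determine pattern of missing data", and a logistic regression "to identify factors associated with incomplete data for survivors". On that model's content it says: "All demographics and baseline characteristics will be included in the logistic model". The team will also "institute corrective measures if the response rate falls below 75" per cent.
- **Section 9.0** adds weekly contact, completion by telephone, and a record of why a packet was not completed.

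**The concern.** Sections 11.3 and 11.4 credit the same property to two different models, and only one of those models is in the plan. Nor does the property carry over. A correctly specified likelihood mixed model is valid when data are missing at random. An unweighted GEE generally needs missingness to be completely at random or to depend only on covariates in the model.

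The planned adjustment for pre-exposure QOL deals with non-response driven by baseline. It does not deal with non-response driven by how the patient felt at the previous follow-up visit. The drop-out plots and the logistic model could reveal such a pattern, but no estimate uses them, and earlier follow-up QOL is not named as a predictor.

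At stake is the QOL contrast between HCT and conventional therapy, which Section 3.4 describes as important for decision-making.

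**Working it through.** The plan gives no QOL effect size, SD, correlation or power, so there is no stated figure to reproduce.

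**Why the property fails.** GEE solves Σ D′V⁻¹R(Y − μ) = 0 over observed scores (R = 1). This is centred on the truth if E[Y − μ | R, X] = 0. If R at visit t depends on Y at visit t−1, and that earlier score is not in the model, the condition generally fails. Replacing R by R/π, with π the response probability given the observed history, restores it under missing at random. So does a correct model for the joint distribution of the repeated scores.

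**Inputs from the documents.** 170 HCT and 505 non-HCT patients (Section 11.1); four follow-up QOL visits after the pre-exposure score (8.1.14); 75% response (the 11.4 action trigger, used here as last-visit response).

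**Assumed.** No true difference; SD 15; AR(1) correlation 0.75; monotone dropout with logit P(respond at t) = a + b × (score at t−1)/15, where b differs by group and a is set to give 75% response at the last visit; HCT status fixed; all patients alive.

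**Last-visit bias in points,** by b in HCT / non-HCT:

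| Analysis | 0/1 | 0.5/1 | 1/0.5 | 1/0 |
|---|---|---|---|---|
| Independence GEE, baseline by visit | −1.10 | −0.47 | 0.59 | 1.18 |
| Independence GEE, one common baseline slope | −0.55 | −0.22 | 0.32 | 0.62 |
| Exchangeable GEE, one common baseline slope | 0.48 | 0.22 | −0.17 | −0.44 |
| Exchangeable GEE, baseline by visit | −0.18 | −0.11 | 0.05 | 0.17 |
| Unstructured GEE, baseline by visit | −0.02 | −0.03 | −0.02 | 0.01 |
| Change-score t-test | 0.66 | 0.32 | −0.24 | −0.60 |
| Independence GEE, baseline by visit, correct response weights by group | 0.03 | 0.04 | 0.06 | 0.03 |

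The exchangeable and unstructured rows with baseline by visit come from separate runs of the same design. Repeats at 0/1 and 1/0 gave −0.29/0.15 for exchangeable and −0.12/−0.01 for unstructured. With 150,000 per group, the simulation error is about 15 × √(2/112,500) = 0.06 points, so values near 0.1 cannot be told from zero. With slopes 0/0 or 1/1, the analyses checked were within 0.07.

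**Scale.** With 127.5 and 378.75 responders (75% of 170 and 505), the unadjusted SE is 15 × √(1/127.5 + 1/378.75) = 1.54 points. The simulated SD of the unweighted estimate was 1.48-1.50. A bias of 1.18 is 1.18/1.49 = 0.79 SE, so the two-sided 5% error becomes Φ(−1.17) + Φ(−2.75) ≈ 12%. Simulated false-positive rates:

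- independence GEE, baseline by visit: 6.8-13.0%
- independence GEE, common slope: 5.7-7.4%
- exchangeable GEE, common slope: 5.8-6.6%
- weighted: 5.0-6.0%
- equal dropout: 4.7-6.0%

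**Sensitivity of the first row.** At 85% or 65% response the bias is 0.3-0.7 or 0.7-1.6 points. With 50% or 35% alive it is 0.5-1.1 or 0.4-1.1. Those survival values are the ends of the three-year range that Section 2.0 gives after nonmyeloablative HCT; applying them to both groups is an assumption.

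**What the weights need.** In the baseline-by-visit model, weights from baseline QOL alone left 0.5-1.2 points. Weights with group and last QOL but no interaction left 0.6-1.3. Neither is better than no weights.

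**What missing-at-random methods cannot do.** If response depends on the current score (slopes 1/0 and 1/0.5), the unweighted bias is 2.0 and 0.9 points, and weighting leaves 1.3 and 0.6.

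**Deaths.** With deaths tied to QOL in one group only (slopes 1/0, 50% alive, no missing scores among the living), the survivors' baseline-adjusted contrast was 2.3 points, and a mixed model gave about 0. The model therefore also decides whose QOL is being estimated.

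**The case against.** The strongest reply is that the problem is small and largely a matter of specification. Much of this stands.

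- An unstructured covariance with pre-exposure QOL by visit removes nearly all the bias under missing at random without any response model. A mixed model of the kind Section 11.4 mentions would be valid under missing at random if correctly specified. The fault there is that it is undefined, not that it has been shown to be biased.
- The largest figures belong to independence GEE with baseline by visit, which the plan does not prescribe. Its remark about within-patient correlation may point to a modelled correlation instead.
- Section 11.4 is not silent. It has monitoring, a trigger, plots by group and a missingness model, and Section 9.0 has active follow-up. The t-tests and GEE are layered, not in conflict.

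Three stronger readings are tempting and unsupported. First, a reader might infer that independence and exchangeable GEE always err in opposite directions. That appears only with one common baseline slope; with baseline by visit they err in the same direction and the exchangeable bias is small. Second, a reader might infer that response weights are the required remedy. They are one option. Third, a reader might infer that the QOL comparison will be biased. The documents do not show that QOL-related dropout will occur or differ by group.

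What the reply does not remove is that the stated property is wrong for the analysis named, and that the model said to supply it is absent.

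**Conclusion.** The point holds and should be fixed before the QOL data are analysed, though the likely bias is modest. Under the assumptions listed, the last-visit bias is:

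- about 0.5-1.2 points (0.03-0.08 SD) for independence GEE with baseline by visit
- 0.2-0.7 for independence or exchangeable GEE with one common baseline slope
- at most about 0.3 for exchangeable GEE with baseline by visit
- about 0.1 or less for an unstructured covariance with baseline by visit, or for correctly specified response weights
- about zero when dropout is unrelated, or equally related, to QOL in both groups

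The SD, correlation, dropout slopes and monotone pattern are assumed. The 75% is an action trigger, not a forecast. HCT was treated as fixed although the plan treats it as time-dependent. The conclusion about the text does not depend on these values: the plan leaves open choices that move the bias from negligible to about 0.08 SD.

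**What to change.** Name the same single longitudinal QOL model in 11.3(3)(i) and 11.4, with group, visit, group by visit and pre-exposure QOL by visit. Replace the claim about missing patterns in both sections with an explicit missing-at-random assumption. Then choose one of two forms:

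1. A linear mixed model (or GEE) with unstructured covariance, stating that it implicitly extrapolates beyond death.
2. If the target is patients alive at each visit, an independence GEE with inverse-probability-of-response weights. The logistic model should be parsimonious: last observed QOL, group, their interaction, KPS and disease status.

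For form 2, do not carry over the 11.4 rule of including every baseline variable. On the inputs above, only about 170 × 0.50 × 0.25 = 21 or 170 × 0.35 × 0.25 = 15 living HCT patients would be missing at the last visit, while 8.1.1 alone lists 12 items.

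In either case, report deaths alongside, label the t-tests descriptive, and add a missing-not-at-random shift analysis by group, informed by the recorded reasons for non-completion.

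The cost is SAP wording and modest analysis work, with no new data. Weighting widened intervals by 0-7% in the simulation, which assumed a correct weight model.

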2.0 INTRODUCTION

The nature of acute myeloid leukemia (AML) changes with age. Different cut-offs have been used to define older AML patients, the most common has been age ≥ 60 years. When compared with younger adults, AML in patients aged ≥ 60 years is more frequently preceded by a myelodysplastic syndrome (MDS), has unfavorable cytogenetics, more commonly expresses multidrug resistance, and hence responds less well to chemotherapy [1-3]. In addition, older AML patients are frailer with poor performance status[3] and probably higher comorbidity burden similar to other aging populations [4-6]. As a result, treating aging individuals with AML has been a challenge with only $\leq 10\%$ patient surviving longer than 5 years.

The advent of nonmyeloablative or reduced-intensity conditioning regimens in the past decade has broadened the eligibility criteria for allogeneic HCT to include older and medically infirm patients. Preliminary data on nonmyeloablative allogeneic HCT among small numbers of older AML patients shows 35-50% survival rates at 3-years, better than expected with conventional chemotherapy [7]. However, extrapolation of these results to the general older AML population is difficult, as they include only those patients who were enrolled onto the HCT protocols. Likewise, patients with a relatively high burden of comorbidities are likely excluded from allogeneic HCT, with this selection bias confounding interpretation of HCT results. The percentages of patients not referred for HCT because of lack of insurance coverage, rapidly progressing disease, poor general condition, or physician preference are unknown.

Our primary goal here is to investigate how often older and medically infirm patients, who are diagnosed with AML or high-risk myelodysplastic syndromes (MDS) and treated with induction therapy, undergo allogeneic HCT in four collaborating institutions. We will investigate different factors that might affect the rate of referral to allogeneic HCT. These rates and reasons will be compared to those in younger and healthier AML/MDS patients. Understanding selection bias, we will follow the prospectively enrolled patients for additional 24 months and describe their outcomes comparing allogeneic HCT versus conventional therapy.

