3. BACKGROUND

3.1 AML in older patients:

In 2006, an estimated 13,410 individuals (7,060 men, 6,350 women) in the United States (US) developed AML, while another 8,990 individuals (5,020 men, 3,970 women) died from the disease [8]. AML is a disease of the elderly with a median age at diagnosis of 68 years. While the average annual incidence of AML is approximately 3.43 per 100,000, it increases progressively with age, to a peak of 55.1 per 100,000 at age ≥ 65 [9]. Moreover, demographic changes in the US population suggest that patients ≥ 65 years old will constitute 20% at 2030 and they will experience a 77% increase in diagnoses of AML between years 2010 and 2030 [10]. Thus, establishing novel criteria for outcome prediction among older AML patients has become an important future goal.

Research on anti-leukemia therapy and improvements in supportive care in the past three decades has resulted in relative improvement in the outcomes of AML with 5-year survival of about 20%.[9]. Nevertheless, the progress in treating older patients with AML has been very limited [11], with 5-year survival rates of only 5.3% and 1.6% for patients aged 65-74 and ≥ 75 years compared to 45.5% for those < 45 years, respectively [9]. There are many presumed reasons for the poor outcomes among older AML patients. When compared with younger adults, AML in patients aged ≥ 60 years is thought to be more aggressive given more frequent antecedent blood dyscrasias, more frequent unfavorable cytogenetic abnormalities, more common expression of multi-drug resistance proteins such as P-glycoprotein, and hence poor response to chemotherapy.[1-3]

Protocol 2368.00

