On the other hand, older AML patients might experience relatively high day-30 NRM (up to 25% [12] compared to 0-10% among younger patients) [3,12]. These results have limited the accrual of older AML patients to clinical trials exploring novel or higher intensity treatments, resulting in sub-optimal therapy of their leukemia. Whether age per se or its interaction with other risk factors is responsible for the high NRM is not really known. For example, poorer performance status was associated with increased mortality among older patients in the Southwest Oncology Group (SWOG) retrospective study [3]. Biological aging is hypothetically composed of three parameters: age, physical function, and organ comorbidities. Indeed, among 427 cancer patients, age, functional impairment, and comorbidities were found to independently predict patient survival regardless of the type of cancer [13]. To date, the role of comorbidities in the decision-making for treatment of older AML patients has not been carefully analyzed.

3.2 Comorbidities and Cancer:

Comorbidities are likely the main factor behind morbidity and mortality after treatment of older patients with cancer. This is in particular since First; in a 'typical' geriatric series, individuals, who are 65 years of age and older suffer on average from three different diseases [4]. Secondly, previous research has demonstrated that severity of a given comorbidity could significantly alter the type of initial anti-cancer treatment. For example, Van Spronsen et al determined that 50% and 15% less chemotherapy were administered to older patients with Hodgkin and non-Hodgkin lymphomas and comorbidities, respectively, when compared to those without comorbidities [14]. In addition, age and comorbidities have been identified as prognostic factors for long-term QOL of cancer patients [15-19]. Comorbidity has an independent impact from functional status and, therefore, could provide additional prognostic information in older cancer patients [20].

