truly nonmyeloablative conditioning regimens have been introduced to reduce toxicities and mortality that can be associated with high-intensity conditioning [33-41]. The new regimens rely in part or entirely on graft-versus-leukemia effects for tumor eradication. Many phase II trials of RIC regimens have been published (reviewed in [42]). These regimens allowed older patients, those who failed preceding high-dose HCT, and those with comorbidities to undergo allogeneic HCT.

In two registry studies, investigators analyzed outcomes of older patients diagnosed with AML or myelodysplastic syndromes (MDS) and treated with various reduced-intensity regimens followed by allogeneic HCT. In a study from the European Group of Blood and Marrow Transplantation [43], 449 patients >60 years old had 4-year NRM of 39% and OS of 27%, which were not statistically significantly different from those of younger patients. In the study from the Center of International Blood and Marrow Transplantation Research (CIBMTR), [44] 376 patients >60 years had 2-year NRM of 34% and OS of 34%. Neither study included information on patients' medical comorbidities.

[figure not shown]
The Seattle Consortium includes 23 collaborating institutions which have enrolled 372 patients aged ≥ 60 years into 21 prospective clinical trials investigating allogeneic HCT after nonmyeloablative conditioning regimen of 2 Gy total body irradiation alone or with fludarabine 90 mg/m². Overall, the cumulative incidence of NRM and the rate of relapse were 27% and 41%, respectively, leading to OS and DFS of 35% and 32%, respectively.

Patients did not statistically significantly differ in these outcomes when stratified by age groups of 60-65, 65-70, or >70 years, while HCT-CI scores predicted increased NRM (**Figure 1**). At 5-years, 67% of living patients were entirely well while 33% continued on immunosuppressive medications for chronic GVHD with a median performance status of 90% for both cohorts. Comorbidities and disease risks for relapse, but not age, were the main predictors for survival. In a risk-stratification model, patients with low relapse risk and no comorbidities had 5-year OS of 69%. We concluded that with the use of nonmyeloablative conditioning, age is no longer a barrier to allogeneic HCT. [45]

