5.3 Tertiary objectives

- 5.3.1 Preliminary therapy data will be used to develop standardized criteria for the definitions of “intensive” and “less-intensive” treatments. Physicians from around the world will be surveyed about their opinion of the intensity of regimens.

Protocol 2368.00

- 5.3.2 Project results will be disseminated per funding agency's request using novel methods. Methods will include social media, websites, videos, and newsletters. Patients may be asked to appear on video. All methods have the possibility of being published or mentioned in publications.
- 5.3.3 Among a subset of patients admitted to the ICU at any time point after induction chemotherapy, evaluation of risk factors associated with 90-day and overall survival after ICU admission. Rates of palliative care referrals in patients with and without ICU admissions will be examined.
- 5.3.4 Comparison of outcomes between patients with secondary AML and patients without secondary AML.

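### Low-severity free improvement, tertiary objective only: the secondary versus primary AML comparison leaves age out of its adjusters and may carry residual confounding by age, of a size the documents cannot give

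*Combined protocol and SAP*

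**What the plan says.** Objective 5.3.4, a tertiary objective, is the "Comparison of outcomes between patients with secondary AML and patients without secondary AML". The only analysis text for it is section 11.3(4)(ii), which evaluates outcomes "after adjusting for percent blasts in the peripheral blood, white blood cell count, and performance status at time of presentation". That gives three adjusters: peripheral-blood blasts, white cell count and performance status. Nothing in the sentence leaves the list open. The broader wording in 11.3(2)(i), which does include age and further unnamed variables, belongs to the comparison of HCT with conventional therapy.

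Elsewhere the document says the following about age:

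- Section 2.0 states that AML at 60 years or older more often follows MDS. Section 3.1 adds that AML at these ages is "thought to be more aggressive given more frequent antecedent blood dyscrasias".
- Section 3.1 gives 5-year survival of "only 5.3% and 1.6% for patients aged 65-74 and ≥ 75 years compared to 45.5% for those < 45 years". It also cites a cohort of 427 cancer patients in which "age, functional impairment, and comorbidities were found to independently predict patient survival regardless of the type of cancer".
- Section 4.0 lists age first among the outcome-discriminative criteria to be collected. Performance status and high white cell count are on the same list.
- Section 8.1.1.2 records age at enrolment.

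**The concern.** A confounder is related to both exposure and outcome and is not caused by the exposure. On the protocol's own account age plausibly meets this description: it is associated with antecedent MDS and with survival, and secondary AML cannot cause age. Age also varies widely here, since eligibility runs from 18 to 80 years (6.1.3, 6.2.2) and section 11.1 expects half of the patients to be 60 or older.

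If age still affects outcome after blasts, white cell count and performance status are in the model, part of that effect would be reported as an effect of secondary AML. With an adverse age effect in all enrolled patients, secondary AML would look worse than it is.

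**Working it through.** **No figure to reproduce.** The documents give no sample size, effect size, alpha or power for this comparison. They give neither the frequency of secondary AML, overall or by age, nor an age hazard ratio adjusted for the three named covariates. What follows is an illustration, not an estimate.

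**Inputs**

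- From section 11.1: 50% of enrolled patients aged 60 or older.
- Assumed: no true effect of secondary AML; secondary AML in a share q of 15-35% of patients; odds ratio (OR) 1.5-3 between secondary AML and age 60 or older; residual age hazard ratio (HR, 60 or older versus younger, given the three adjusters) of 1.0-2.0.

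**Formulas.** Let p1 and p0 be the shares aged 60 or older in secondary and primary AML.

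- p1 = OR × p0 / (1 − p0 + OR × p0)
- q × p1 + (1 − q) × p0 = 0.50, solved for p0
- Spurious ratio ≈ [1 + p1 × (HR − 1)] / [1 + p0 × (HR − 1)]

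**Results at q = 25%**

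| OR | p0 | p1 | HR 1.0 | HR 1.3 | HR 1.5 | HR 2.0 |
|---|---|---|---|---|---|---|
| 1.5 | 0.475 | 0.576 | 1.00 | 1.03 | 1.04 | 1.07 |
| 2 | 0.457 | 0.628 | 1.00 | 1.04 | 1.07 | 1.12 |
| 3 | 0.434 | 0.697 | 1.00 | 1.07 | 1.11 | 1.18 |

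For example, OR 3 and HR 2.0 give (1 + 0.697) / (1 + 0.434) = 1.18.

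Varying q over 15-35% gives 1.03-1.07 at HR 1.3 and 1.07-1.19 at HR 2.0. At HR 1.0 the ratio is exactly 1.00 throughout.

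**Why the survival figures in section 3.1 do not supply the HR.** On the cumulative-hazard scale they give ln(0.053)/ln(0.455) = 3.7 for 65-74 years versus under 45, and ln(0.016)/ln(0.455) = 5.3 for 75 or older versus under 45. These are unadjusted contrasts of extreme age groups. The same section attributes part of older patients' poor outcome to antecedent blood dyscrasias, so some of the gradient may be the exposure itself.

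**The case against.** The strongest reply is that the documents do not show an age effect beyond the three adjusters.

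- The section 3.1 survival gradient is unadjusted, and the statement that age predicts independently comes from a general cancer cohort, not from AML.
- On early mortality, section 3.1 says: "Whether age per se or its interaction with other risk factors is responsible for the high NRM is not really known".
- Section 3.3 reports a European registry study in which NRM and OS of HCT recipients over 60 were outcomes "which were not statistically significantly different from those of younger patients", and a consortium series in which age was not a main predictor of survival.
- Section 2.0 says older AML patients have poor performance status, which is already an adjuster.
- The age link is given for antecedent MDS or blood dyscrasias. The supplied text does not define secondary AML, so the link may not cover the whole exposure group.

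Most of this stands, and it is why the conclusion is only that confounding may remain. It does not remove the point. The section 3.3 results concern selected HCT recipients: the consortium series included only patients of 60 or older, and the registry paper's title in the reference list limits it to 50 or older. Neither tests age from 18 to 80 among all AML patients. Performance status can carry only part of an age effect, and the cancer cohort reports age as independent of functional impairment.

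It could also be argued that 11.2(5) brings age in, since it carries significant variables into subsequent comparisons. That rule sits in the models for undergoing HCT. Even on a broad reading it would make age conditional on a P-value threshold there. It does not place age in the model for secondary AML.

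A reader might infer that the comparison will be biased against secondary AML, or that the section 3.1 gradient shows a large bias. The documents support neither: the first needs a residual age effect that they do not establish, and the second treats crude contrasts as adjusted ones.

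**Conclusion.** The point holds as a low-severity free improvement to a tertiary analysis. Age is omitted from a closed adjustment list, although the protocol treats it as related to antecedent MDS and to outcome and already collects it. Residual confounding by age is possible but not demonstrated.

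Its size is not derivable from the documents. It is nil if age adds nothing to the three adjusters or is unrelated to secondary AML. Otherwise the inflation is about 1.03-1.19 in all enrolled patients, for a survival-type outcome and residual age HRs of 1.3-2.0. Only the 50% aged 60 or older is a protocol figure; every other input is assumed.

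It is tempting to carry this range and direction over to the older or medically infirm cohort named in the 11.3 heading. The documents do not support that. Patients under 60 enter that cohort only through a comorbidity score of 3 or more (11.1), so age and comorbidity are tied together by selection. No size or direction is claimed there. No primary or secondary conclusion is affected.

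**What to change.** Add age at enrolment to the adjusters in 11.3(4)(ii), preferably as a continuous variable, or state why it is left out. Say which population is analysed: objective 5.3.4 reads as all patients, while the analysis sits under a heading limited to older and medically infirm patients. If it is restricted to that cohort, adjust for enrolment HCT-CI as well as age, because entry is by age or by comorbidity score.

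The cost is about one line of text and a few model terms. Age (8.1.1.2) and HCT-CI (8.1.4.4) are already collected at enrolment, so no new data, visits or patients are needed. Making the change before analysis also avoids a post hoc choice of covariates.
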